The PASI has been developed to provide quantitative assessment of psoriasis lesional burden based on the amount of BSA involved and degree of severity of erythema, induration, and scale, weighted by body part. The head, upper extremities, lower extremities, and trunk are assessed separately and then combined using weighting based on the surface area represented by each area (head 0.1, upper extremities 0.2, trunk 0.3, and lower extremities 0.4). The degree of erythema, induration, and scale in each area is judged on a 0–4 scale, the sum of which represents disease severity. The area of involvement of each area is graded from 0–6, depending on the estimated percentage of lesion area (0: 0 %, 1: 0-10%, 2: 10-29%, 3: 30-49%, 4: 50-69%, 5: 70-89%, and 6: 90-100%). These body scores are multiplied by the disease severity score and the weighting for each body area, yielding a score between 0 and 72^{10} .

Harvey-Bradshaw Index (HBI):

The Harvey-Bradshaw index is a score for quantification of symptoms in patients with CD. It consists of only clinical parameters:

general well-being (0 = very well, 1 = slightly below average, 2 = poor, 3 = very poor, 4 = terrible)

_ 14

Confidential Information

No use or disclosure outside AbbVie is permitted without prior written authorization from AbbVie

abdominal pain (0 = none, 1 = mild, 2 = moderate, 3 = severe) number of liquid stools per day abdominal mass (0 = none, 1 = dubious, 2 = definite, 3 = tender) complications, as above, with one point for each.

The values can range from 0 (in healthy subjects) to 30 points, whereas moderate to severe patients have Harvey-Bradshaw index \geq 7. A score of less than 5 is generally considered to represent clinical remission¹².

Partial Mayo score (PMS)

For the evaluation of the patient's disease activity the partial Mayo score will be documented at each visit. In this study, an average score of five measurements (see subscore sections) shall be used for analysis. The partial Mayo Score has been proven to be a valid and reliable noninvasive measure to evaluate disease activity in adults with UC¹³. If endoscopy is routinely performed during the visit the full mayo score can be documented¹⁴. (Please see definition of Mayo Score below)

The Mayo Score is a composite of the following subscores: Stool Frequency subscore, Rectal Bleeding subscore, Endoscopy subscore, and Physician's Global Assessment subscore¹³.

The Partial Mayo Score is a composite of the following subscores: Stool Frequency subscore, Rectal Bleeding subscore, and Physician's Global Assessment subscore¹⁴.

Stool Frequency Subscore

The stool frequency subscore is calculated by comparing the stool frequency to a reference number. The reference number is the number of stools per day (24 hours) that is typical for the subject when having active UC but not experiencing a flare and needs to be designated once prior to enrollment. The reference number should represent a full number of at least 1.

Subjects will record the daily number of stools throughout the trial. Using these numbers, the Stool Frequency subscore will be assessed for each study day as follows:

A number of bowel movements lower than or equal to the reference number of bowel movements should be scored as 0 = Normal.

Confidential Information

One or 2 bowel movements more than the reference number of bowel movements should be scored as 1.

Three or 4 bowel movements more than the reference number of bowel movements should be scored as 2.

Five or more bowel movements more than the reference number of bowel movements should be scored as 3.

The Stool Frequency subscores from the 5 days prior to each study visit will be averaged and used for the Stool Frequency subscore for each study visit.

The Stool Frequency subscore during days which the subject received anti-diarrheal medication will be scored as a 3.

Diary entries for stool frequency should not be included in the 5 days prior to the visit that are evaluated for the Stool Frequency subscore for the following days: (1) the day the subject received medication for bowel preparation prior to endoscopy, (2) the day the subject underwent an endoscopy, and (3) 2 days following the endoscopy. Earlier diary entries will be used accordingly in order to provide the most recent data for 5 days prior to the respective study visit.

Rectal Bleeding Subscore

Subjects should record a daily rectal bleeding subscore value as follows:

No visible blood with stool during the respective day should be scored as 0.

Visible blood with stool less than half the time during the respective day should be scored as 1.

Visible blood with stool at least half the time during the respective day should be scored as 2.

A score of 3 for bleeding requires subjects to have at least 50% of bowel movements accompanied by visible blood and at least one bowel movement with blood alone.

_ 16

Confidential Information

The score entries into subject's diary from the 5 days prior to each study visit will be averaged and used for the Rectal Bleeding subscore for each study visit.

Diary entries for rectal bleeding should not be included in the 5 days prior to the visit that are evaluated for the Rectal Bleeding subscore for the following days: (1) the day the subject received medication for bowel preparation prior to endoscopy, (2) the day the subject underwent an endoscopy, and (3) 2 days following the endoscopy . Earlier diary entries will be used accordingly in order to provide the most recent data for 5 days prior to the respective study visit.

Physician's Global Assessment Subscore

The physician's global assessment acknowledges the 2 subject-reported subscores, the endoscopy subscore as applicable, the subject's daily record of abdominal discomfort (pain/cramps) and general well-being during the 5 days prior to the visit, and other observations such as physical findings, and the subject's performance status in order to assess disease activity as follows:

0 = Normal 1 = Mild disease 2 = Moderate disease 3 = Severe disease

Endoscopy Subscore

The endoscopist should evaluate each observed segment of the colon (rectum, sigmoid, descending colon, transverse colon, ascending colon/cecum) by using the classification as follows:

- 0 = Normal or inactive disease
- 1 = Mild disease (erythema, decreased vascular pattern, mild friability)
- 2 = Moderate disease (marked erythema, absent vascular pattern, friability, erosions)
- 3 = Severe disease (spontaneous bleeding, ulceration)

Confidential Information

The endoscopic subscore for the subject will be the worst score of the observed segments.

The local endoscopist should also separately assess presence or absence of friability (yes/no).

The endoscopy will be recorded on a videotape and will undergo a central review process for endoscopy subscore assessment.

C-reactive protein CRP:

The CRP is an acute phase reactant plasma protein, normally produced by the liver, which is commonly used as an indirect measure of the extent and activity of an inflammation. Synthesis of this protein increases rapidly in response to inflammatory stimuli in both acute and chronic settings. After the inflammation is over the CRP level is rapidly decreased again. The normal reference range in the blood is as a rule from 0 to 1,0 mg/dl CRP. The CRP is increased in a variety of disorders like rheumatic diseases.

Erythrocyte sedimentation rate (ESR):

The ESR is based on the sedimentation and aggregation of erythrocytes. It is influenced due to the large and asymmetric plasmaproteins as immunoglobulins, fibrinogen and α 2-macro-globulin. These plasmaproteins favour the production of erythrocyte aggregates which sediment faster than every single erythrocyte. The ESR is a practicable and sensitive but not specific parameter for measuring disease progression. By means of the ESR it can be generally distinguished between an active and non-active rheumatic disease. The normal reference range is as a rule for men 0 – 10 mm/h and for women 0-15 mm/h.

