The PASI score for each body region is obtained by multiplying the sum of the severity scores by the area score, then multiplying the result by the constant weighted value assigned to that body region. Since the head, upper extremities, trunk, and lower extremities correspond to approximately 10, 20, 30, and 40% of body surface area, respectively; the PASI score is calculated using the formula

$$PASI = 0.1(E_h + I_h + D_h)A_h + 0.2(E_u + I_u + D_u)A_u + 0.3(E_t + I_t + D_t)A_t + 0.4(E_l + I_l + D_t)A_l$$

where E, I, D, and A denote erythema, inducation, desquamation, and area, respectively, and h, u, t, and l denote head, upper extremities, trunk, and lower extremities, respectively. PASI scores range from 0.0 to 72.0 with the highest score representing complete erythroderma of the severest degree.

Based on articles: Fredriksson T, Pettersson U. Severe psoriasis--oral therapy with a new retinoid. Dermatologica. 1978;157(4):238-44, and Mease, P. J. Measures of Psoriatic Arthritis. Arthritis Care Res, 2011,63(Suppl 11): S64–S85.

Harvey-Bradshaw Index (HBI)

HBI BASED ON PATIENT'S SYMPTOMS IN PREVIOUS 24 HOURS

General Well-Being

0 = very well, 1 = slightly below par, 2 = poor, 3 = very poor, 4 = terrible

Abdominal Pain

0 =none, 1 =mild, 2 =moderate, 3 =severe

Number of Liquid Stools per Day

Abdominal Mass

0 =none, 1 =dubious, 2 =definite, 3 =definite and tender

92

Confidential Information

Complications: (Score 1 Per Item)	
Arthralgia	
Uveitis	
Erythema Nodosum	
Aphthous Ulcers	
Pyoderma Gangrenosum	
Anal Fissure	
New Fistula	
Abscess	

Harvey-Bradshaw Index Score:

<5	remission
5 – 7	mild
8-16	moderate
>16	severe

Based on the article Harvey RF, Bradshaw JM. A simple Index of Crohn's disease activity. Lancet 1980; 1:514.

Partial Mayo score (PMS)

Based on Patients symptoms in previous 24 hours	Score	
Stool Frequency		
0 = normal,		
1 = 1 to 2 stools per day more than normal	3 6 - 1 33	
2 = 3 to 4 stools per day more than normal		
$3 = \ge 5$ stools per day more than normal		
Rectal Bleeding		
0 = No Blood seen		
1 = Streaks of blood with stool less than half the time	8 	
2 = Obvious blood with stool most of the time		
3 = Blood alone passes		
	93	

Confidential Information

abbvie	Adalimumab P13-562 Protocol	
Physician's Glo	bal Assessment	
0 = Normal		
1 = mild disease	9	
2 = moderate di	sease	
3 = severe disea	ise	
	3-4 mild; 5-6 moderate; \geq 7 severe TOTAL	
Was Endoscopy	γ performed in this Visit? \Box yes \Box no	
If Yes:		

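### Section 6.5.1 and the eCRF score the Partial Mayo score in UC by different rules: the stool reference, bleeding grades and time window do not match

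*Combined protocol and SAP*

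**What the plan says.** **Status of the score.** Sections 5.2 and 11.1.2 list change in the Partial Mayo score (PMS) for UC, and change in the Harvey-Bradshaw Index (HBI) for Crohn's disease, among the secondary endpoints.

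**Stool subscore.** Section 6.5.1 fixes a reference number once before enrolment: the daily count "typical for the subject when having active UC but not experiencing a flare". A count "lower than or equal to the reference number of bowel movements should be scored as 0 = Normal", and "One or 2 bowel movements more than the reference number of bowel movements should be scored as 1". The eCRF in Appendix D uses the same steps but another anchor: "1 = 1 to 2 stools per day more than normal" and "2 = 3 to 4 stools per day more than normal". It does not define *normal*, and the text shown has no field for the reference number.

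**Bleeding subscore.** In section 6.5.1, grade 2 is visible blood at least half of the time. Grade 3 needs both blood in at least 50% of bowel movements and at least one movement of blood alone. On the eCRF, grade 2 is obvious blood most of the time, and grade 3 needs only that blood alone is passed.

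**Window.** Section 6.5.1 averages daily stool and bleeding scores over the five days before the visit. The eCRF form is headed as covering the previous 24 hours.

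**HBI label.** Section 6.5.1 states: "The values can range from 0 (in healthy subjects) to 30 points, whereas moderate to severe patients have Harvey-Bradshaw index" of 7 or more. The eCRF class table lists 5 to 7 as mild and 8 to 16 as moderate.

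**The concern.** A change score means something only if both of its ends were scored by one rule. Here an investigator who follows section 6.5.1 and one who follows the form can give the same UC patient different totals, and the recorded number does not show which rule produced it.

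The study is planned at 28 sites (section 6.2). Section 9.0 says that it will not be monitored and that entered data are checked for consistency. A PMS from either rule lies in the allowed range, so such a check need not detect the difference. Variation between sites in how they scored could then be read as variation in disease activity.

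**Working it through.** The plan states no figure to reproduce. The check is to apply both sets of rules as written and compare the results.

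**1. Stool subscore.** With d = stools per day minus the reference, both sources score d ≤ 0 as 0, d of 1–2 as 1, d of 3–4 as 2, and d ≥ 5 as 3. Only the reference can differ. The documents give no patient values, so these are assumptions: ordinary habit 1 stool a day, section 6.5.1 reference 4 a day, eCRF *normal* read as the ordinary habit.

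| Stools/day | Section 6.5.1 (reference 4) | eCRF (normal 1) | Difference |
|---|---|---|---|
| 1 | 0 | 0 | 0 |
| 2 | 0 | 1 | 1 |
| 3 | 0 | 1 | 1 |
| 4 | 0 | 2 | 2 |
| 5 | 1 | 2 | 1 |
| 6 | 1 | 3 | 2 |
| 7 | 2 | 3 | 1 |
| 8 | 2 | 3 | 1 |
| 9 | 3 | 3 | 0 |

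Varying the gap between the two references, with an assumed normal of 1:

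| Gap (stools/day) | Counts at which scores differ | Largest difference |
|---|---|---|
| 0 | none | 0 |
| 1 | 2, 4, 6 | 1 |
| 2 | 2–7 | 1 |
| 3 | 2–8 | 2 |
| 4 | 2–9 | 2 |
| 5 | 2–10 | 3 |

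A normal of 2 gives the same largest differences.

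**2. Effect on the total.** The eCRF classes are ≤ 2 no activity, 3–4 mild, 5–6 moderate, ≥ 7 severe. Take 4 stools a day, bleeding 1 and physician's global assessment 1, with the references of the first table:
- Section 6.5.1: 0 + 1 + 1 = 2, no activity.
- eCRF: 2 + 1 + 1 = 4, mild.

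**3. Bleeding, with no stool reference involved.** Take a hypothetical day with six stools, one of blood alone and five clear.
- Section 6.5.1: 1/6 is about 17%, less than half, so grade 1. Grade 3 is barred because it needs at least 50%.
- eCRF: blood alone was passed, so its wording supports grade 3.

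The difference is 3 − 1 = 2 points. With global assessment 1 and the same stool subscore under both rules, the totals are:
- stool 0: 2 against 4 (no activity, mild);
- stool 1: 3 against 5 (mild, moderate);
- stool 2: 4 against 6 (mild, moderate);
- stool 3: 5 against 7 (moderate, severe).

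The class changes in every case.

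**4. Window.** A mean of five whole-number daily scores is a multiple of 1/5 = 0.2. The eCRF grades are whole numbers. The two windows therefore yield different kinds of value, and the printed classes do not say where a total between 2 and 3, for example, belongs. This needs no assumption about patients.

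**5. HBI.** Comparing the two sources score by score:
- below 5: remission in both;
- 5 and 6: mild on the eCRF, no label in section 6.5.1;
- 7: mild on the eCRF, moderate to severe in section 6.5.1;
- 8 and above: compatible.

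The only contradictory score is 7.

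**The case against.** The strongest reply is that the stool rules may not differ at all. Section 6.5.1 itself labels a count at or below its reference as normal, and the eCRF uses that word with the same steps. A site may take the two as one thing, and its stool subscores are then identical. This stands: a reader might infer that two different reference levels are established, but the documents show only an undefined term that allows two readings. It does not remove the bleeding and window differences.

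Other stronger readings also go beyond the text:

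- *One site may switch rules between visits.* Nothing describes this. Section 6.5.1 fixes the reference once, and all sites enter data on the same eCRF.
- *The section 6.5.1 reference hides the improvement to be expected on treatment.* Counts below the reference do all score 0, but a fall from above it still registers, as do bleeding and the global assessment. The documents do not say how many patients start at or below the reference.
- *The HBI conflict changes an endpoint or eligibility.* The endpoint is numerical change, sections 11.1.2 and 11.2 specify no analysis by HBI class, and section 6.1.1 uses no HBI threshold.
- *The 30-point HBI range is a material error.* The other items total at most 4 + 3 + 3 + 8 = 18, so passing 30 takes 13 liquid stools with every other item at its maximum. No range check is described. It is trivial.

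It is also fair that the endpoint is secondary and descriptive, section 11.2 allows no working hypothesis, and the study is mainly about beliefs and adherence.

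**Conclusion.** The concern holds for the Partial Mayo score. Stool reference, bleeding grades 2 and 3, and time window are stated differently in section 6.5.1 and on the eCRF, and the PMS value can depend on which is followed.

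The stool part is worth 0 to 3 points over assumed gaps of 0 to 5 stools a day. It is zero if sites read *normal* as the section 6.5.1 reference. The bleeding part is worth 2 points in the example and needs no stool reference, though how often such a day occurs is unknown. The documents do not settle which reference, grading or window is right.

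The reach is limited to the UC share of about 30 Crohn's and UC patients combined (section 6.2), a split that the protocol does not give. The correction should be made, but it does not threaten the study's main objective. The HBI disagreement at 7 is a labelling matter that leaves numerical change in HBI untouched.

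**What to change.** 1. Reconcile section 6.5.1 with Appendix D so that one stool reference, one set of bleeding grades and one time window appear in both. The sponsor must choose and define them.
2. State the chosen rule in the data analysis plan, which section 11.2 promises before the analysis.
3. Ask sites which stool reference, bleeding wording and window they used for UC patients. A new Visit 1 field would not be enough: this protocol version is dated 27 Oct 2016, and section 6.4 estimated the end of inclusion as September 2016.
4. Rescore where the reference used can be established and the underlying counts are available, for example from the daily records described in section 6.5.1. Otherwise flag the value and compute change only within patients scored by one definition throughout.
5. Print one HBI class for a score of 7 in both places.

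The cost is wording changes, queries for the UC patients, and some flagged PMS values that drop out of the change analysis in an already small group.

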3.0 Introduction

The Adherence to biological medication in Rheumatoid Arthritis (RA), Psoriatic Arthritis (PsA), Ankylosing Spondylitis (AS), plaque psoriasis (PsO), Crohn's disease (CD) and ulcerative colitis (UC):

As there exist a lot of variations in the definitions and methodologies of measurement used to characterize adherence - compliance and persistence - first of all it is important to provide a definition for these terms. Compliance or more precisely medication compliance refers to the extent a patient is passively following the physician's orders as acting in accordance with the prescribed timing, frequency and dosage. It is typically measured as a percentage of total number of doses taken in relation to the time period of observation, during which medication compliance is measured ^{1,2}. In the literature an arbitrary cut-off value of 80% is used to distinguish between compliance and non-compliance although it is not clear what the clinically relevant cut-off point is. It is also understandable that the required drugs which are necessary to achieve an optimal treatment goal may be different for each patient and each drug. Therefore some patients may be well controlled with a standard dosage scheme while other patients may require a more frequent administration. Persistence or more precisely medication persistence is the duration of time from the beginning to the discontinuation of the prescribed therapy and is measured in units of time ^{1,2}. Adherence can be considered as an umbrella term for medication compliance and medication persistence as this term involves both perceptions of taking a medication, namely regularity and consistency ^{1,2}. Poor or non-adherence to a drug is a very important aspect in contributing to inadequate response to or failure of treatment and worsening of the disease. In consequence of an insufficient adherence clinical outcomes will deteriorate and may prompt a physician to further diagnostic procedures and eventually to an unnecessary change in medication³. Clearly this may lead to a longer patient recovery period and increased healthcare costs. This raises the question: how can we improve adherence in those patients who are afflicted with chronic inflammatory diseases like RA, AS, PsA, PsO, CD or UC? The answer is not easy because adherence is a complex phenomenon and it can both be difficult to identify factors associated with nonadherence and applying help in an effective manner. In clinical studies about tight control such factors can be easier identified and patients can therefore be more intensively motivated to be

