6.0 Investigational Plan

6.1 Selection of Study Population

The study P13-562 is a non-interventional, observational study in which HUMIRA[®] is prescribed in the usual manner in accordance with the terms of the local marketing authorization with regards to dose, population and indication. The assignment of the patient to a HUMIRA[®] containing regimen has to be decided in advance and has to be current practice. The prescription of HUMIRA[®] is clearly separated from the decision to include the patient in this study! No additional procedures (other than standard of care) shall be applied to the patients.

It is planned to enroll approximately 140 patients in total. All patient data entered in the patient's data report form (CRF) will be forwarded - without naming the patient - for evaluation to AbbVie. In order to maintain patient confidentiality, the patient's age in year, gender and race will be documented in the CRF. The patients must provide written authorization to the investigator to use and/or disclose personal and/or health data before entry into study P13-562.

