9.0 Ethics and Quality

All patient data entered in the patient's electronic data report form (eCRF) will be forwarded - without naming the patient - for evaluation to AbbVie. In order to maintain patient confidentiality, instead of date of birth, the patient's age will be documented in the eCRF.

The patients must provide written authorization to the investigator to use and/or disclose personal and/or health data before entry into this PMOS. The investigator will document this authorization in the patient's chart. There are no local law requirements for monitoring, notification /submission of a post-marketing observational study to an ethics committee and/or regulatory body. However, a written confirmation from one of the Lead–ECs will be obtained. In this the following statement should be documented: "According to §2 paragraph 3 of the Austrian Pharmaceutical Act it is an observational study and therefore an evaluation by the ethics committee (EC) is not required". The protocol and the IC/ADU should be provided to the EC for review. It will be submitted to a regulatory body. The study will not be monitored. However in order to assure professional site data-management a qualified Clinical Research Organisation (CRO) as well as a statistician is assigned. Concretely this means that data entered in the eCRFs by the sites will be checked for consistency of data. Inconsistent data will be queried.

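### For ulcerative colitis, section 6.5.1 asks for a year-long daily stool record and centrally read endoscopy video that section 6.1, the schedule and the eCRF do not support, and the Partial Mayo Score has two scoring windows

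*Combined protocol and SAP*

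**What the plan says.** Section 6.1 describes a non-interventional study in which no "additional procedures (other than standard of care) shall be applied to the patients". Section 9.0 relies on the same status, asking for a written confirmation that "it is an observational study and therefore an evaluation by the ethics committee (EC) is not required".

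The Partial Mayo Score (PMS) text in section 6.5.1 asks for more than this from UC patients:

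- Stool count: "Subjects will record the daily number of stools throughout the trial".
- Rectal bleeding: "Subjects should record a daily rectal bleeding subscore value as follows".
- The physician's global assessment takes into account "the subject's daily record of abdominal discomfort (pain/cramps) and general well-being during the 5 days prior to the visit".
- Scoring: "The Stool Frequency subscores from the 5 days prior to each study visit will be averaged". Bleeding entries are averaged in the same way.
- Endoscopy: "The endoscopy will be recorded on a videotape and will undergo a central review process for endoscopy subscore assessment". The same section documents the full Mayo score only where an endoscopy is done as part of routine care.

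The Schedule of Activities in section 6.5 lists the PMS at all five visits and at early termination, but no diary. The visit descriptions in sections 6.5.2.1 to 6.5.2.3 mention no diary either. The PMS form in Appendix D is headed as covering symptoms in the previous 24 hours. It has a field for an endoscopy finding, but no diary page and no field for a central reading. Change in PMS is a secondary objective (5.2) and a secondary endpoint (11.1.2).

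**The concern.** Two things are at stake.

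The first is the PMS itself. A site that follows section 6.5.1 issues a diary and averages 5 days. A site that follows the eCRF asks about the last 24 hours. Nothing in the eCRF shows which was done, and section 9.0 says the study will not be monitored. A change in PMS could then mix two measurements, between sites or between visits of one patient.

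The second is comparability. None of the other five indications has a daily task; RADAI, BASDAI, PASI and the Harvey-Bradshaw Index are collected at visits. The main objective concerns beliefs and adherence, and section 11.2 plans to compare compliance by patient characteristics. If indication is one of these, diary use is confounded with UC. The protocol is alert to influences of this kind: the remark in section 4.0 says that patient support programs might affect results and puts a question about them in the eCRF. It makes no such provision for the diary.

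**Working it through.** **1. Planned numbers.** Section 6.2 gives 80 RA, PsA and AS, 30 PsO, and 30 Crohn's disease (CD) or UC: 80 + 30 + 30 = 140. It also gives 28 sites with about 5 patients each: 28 × 5 = 140. Both agree with the stated total. There is no power calculation to reproduce.

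**2. The passages side by side.**

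| Item | Section 6.5.1 | Section 6.1, schedule, visit descriptions, eCRF |
|---|---|---|
| Stool count | Daily, whole study | Not listed as a diary; eCRF asks about previous 24 hours |
| Rectal bleeding | Daily, duration not stated | Same |
| PMS window | Average of 5 days | Previous 24 hours |
| Endoscopy | Video and central reading | Finding entered by the site, if endoscopy was done |
| Added procedures | Not described as standard of care | None beyond standard of care |

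**3. How much of the diary the score uses.** Follow-up is at most 12 months (6.4), so the explicit stool record is about 365 entries per patient.

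- All five scheduled visits: 5 × 5 = 25 days; 25/365 = 6.8%.
- Four follow-up visits only: 4 × 5 = 20 days; 20/365 = 5.5%. This count applies if the diary starts at visit 1, because the 5 days before that visit would then have no entries.
- Section 6.5.1 skips the bowel-preparation day, the endoscopy day and the 2 days after it, and uses earlier entries instead. That is at most 1 + 1 + 2 = 4 days for one endoscopy, so a record must reach back at most 5 + 4 = 9 days. Even if this happened at all five visits, 5 × 9 = 45 days; 45/365 = 12.3%.

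**4. How far the two windows can differ.** Each subscore runs from 0 to 3. Take the extreme case of four days at 0 and a last day at 3, with the last day standing for the previous 24 hours. The 5-day average is 3/5 = 0.6 and the 24-hour score is 3, a gap of 2.4. Stool frequency and bleeding together can differ by 2 × 2.4 = 4.8 points, on a total that runs from 0 to 3 × 3 = 9. This is a bound, not an expected difference.

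**5. Weight of UC in the study.** The CD/UC split of the 30 places is not given. Assuming 5 to 30 UC patients, the share is 5/140 = 3.6% to 30/140 = 21.4%. If the diary moved adherence on the Morisky scale (MMAS, range 0 to 4) by an assumed 0.5 points, the pooled mean would move by 0.5 × 5/140 = 0.02 to 0.5 × 30/140 = 0.11. For an assumed 1 point, it would move by 0.04 to 0.21. Within UC, or in a comparison of UC with the rest, the whole assumed shift would appear.

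**The case against.** The strongest reply is that the diary may never have been run. With no diary in the schedule, the visit descriptions or the eCRF, sites may simply have used the 24-hour form. That is fair, and it is why the point is an unresolved contradiction rather than proof that patients kept diaries. It does not remove the problem: section 6.5.1 gives working rules for averaging and for replacing days, so a site could reasonably follow it.

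Four stronger readings are tempting, and the documents do not support them.

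- **Four items every day for a year, 4 × 365 = 1,460 entries.** Only the stool count is tied to the whole study. Bleeding is daily without a stated duration. Discomfort and well-being are mentioned only for the 5 days before a visit.
- **The central reading serves no endpoint.** Section 6.5.1 lets the endoscopy subscore inform the physician's global assessment, which is part of the PMS. What is missing is a place to record the central result.
- **Endoscopy is imposed.** It is scored only when done routinely. The additions are the video and the central reading.
- **The diary biases adherence.** Section 3.0 says "In clinical studies about tight control such factors can be easier identified and patients can therefore be more intensively motivated to be" compliant, but this concerns tight-control studies, not symptom diaries. A stool count records no injections. An effect is possible, but nothing in the documents shows that it exists or how large it is.

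Timing also counts against a wording change alone. UC enrolment began in November 2014, inclusion was expected to end in September 2016 (6.4), and this version is dated 27 October 2016. Much of the UC exposure lies before any correction.

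**Conclusion.** The contradiction stands in the current text. Section 6.5.1 adds a daily patient record and central video reading for UC that section 6.1 excludes unless they are standard of care, which is nowhere stated. The rest of the protocol makes no provision for them. The firm consequence is a secondary endpoint with two incompatible scoring windows and no record of which was used. Over 93% of the explicit stool record would enter no score under the standard 5-day rule (365 − 25 = 340 days; 340/365 = 93.2%).

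The influence on adherence is possible but unquantified. It concerns UC results and comparisons by indication far more than pooled results, since UC is at most 30 of 140 patients, and fewer if any CD patients are enrolled. A reader might infer that the diary undermines the observational status invoked in section 9.0. The documents do not settle that, and it is not claimed here. The verdict assumes 12 months of follow-up and five scheduled visits. It makes no assumption about how many sites issued diaries.

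**What to change.** 1. Reconcile section 6.1, the schedule in 6.5, the PMS text in 6.5.1, the follow-up visit lists in 6.5.2.2 and the Appendix D form on one PMS scoring window, chosen by the sponsor and stated identically in each place.
2. Delete the words in 6.5.1 that extend the stool record over the whole study. Either obtain stool frequency and bleeding at the visit, or limit any patient record to the chosen window. Since physicians set the visit dates and intercurrent visits occur, the visit-based option is easier to run.
3. Delete the video and central-review sentence and use the site's endoscopy score when endoscopy was routine.
4. If diaries were already issued, record per UC patient whether one was kept and, per visit, which PMS window was scored. Report UC adherence and PMS results by diary use where both groups exist. If all or none kept a diary, say so and interpret comparisons by indication accordingly.

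The cost is protocol wording, two data fields, a query to the UC sites for past visits and one descriptive table. Recall at a visit is somewhat less exact than a daily diary. With few UC patients, the split in step 4 can only be descriptive.
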